7.3.2.2. AEs and SAEs by System Organ Class (SOC) and Preferred Term (PT)

The number of AEs and the number and percentage of patients with events will be presented by SOC and PT. SAEs will be summarized similarly.

7.3.2.3. AEs and SAEs by SOC, PT, and Relationship

The number of AEs and the number and percentage of patients with events will be presented by SOC and PT as described above by relationship (related, not related). In addition, AEs will be summarized as not related, unlikely related, possibly related, probably related, or definitely

related. If a patient has more than one occurrence of an AE, the strongest relationship to study treatment will be used in the summary table. SAEs will be summarized similarly.

7.3.2.4. AEs and SAEs by SOC, PT, and Severity

The number of TEAEs and the number and percentage of patients with events will be presented by SOC and PT as described above by severity (grade 1, grade 2, grade 3, grade 4, grade 5). If a patient has more than one occurrence of an AE, the highest grade will be used in the summary table.

7.3.2.5. Deaths, Other SAEs, and Other Significant Adverse Events

A listing of patient deaths will be produced, if applicable.

7.3.3. Other Safety

7.3.3.1. Analyses for Laboratory Tests

Descriptive statistics by visit will be presented for each central laboratory parameter and for changes from Baseline (continuous variables), by cohort and overall. Baseline is defined as the last non-missing assessment value prior to the first ALXN1210 infusion. Shift tables over time will be presented for all central laboratory values, where applicable, using grading criteria from CTCAE v4.03. For purposes of analyses, laboratory results based upon standardized units will be used. Individual patient plots as well as box plots will be presented for the following central lab parameters: hemoglobin, free hemoglobin, hematocrit, reticulocytes, LDH, bilirubin, creatinine AST, ALT and GGT.

All central and local laboratory data will be presented in by-patient listings.

7.3.3.2. Vital Signs

Absolute values and changes from baseline in vital signs (blood pressure, heart rate, respiratory rate, and temperature) will be summarized descriptively at each visit, by cohort and overall. Baseline is defined as the last non-missing assessment value prior to the first ALXN1210 infusion. A listing of vital signs will be presented.

7.3.3.3. Electrocardiograms (ECG)

The average of the triplicate ECG reading, where applicable, will be calculated and descriptive statistics by visit will be presented for each ECG parameter (including PR, QRS, QT, and QTcF) values and for change from baseline values. The mean of the three pre-dose readings will be considered the baseline values for each patient. If values are not available for all three readings, an average will be calculated based on the available non-missing values. For records with missing RR, HR will be used to calculate RR as defined in Section 9.4 An outlier analysis will be performed that will summarize the frequency and percentage of subjects who meet any of the following outlier criteria:

- QT, QTcF interval >450 msec

- QT, QTcF interval >480 msec
- QT, QTcF interval >500 msec
- QT, QTcF interval increases from baseline >30 msec
- QT, QTcF interval increases from baseline >60 msec

A listing of ECG results will be presented.

7.3.3.4. Non-Drug Therapies and Procedures

By-patient listings of non-drug therapies and procedures will be produced.

7.3.3.5. Infusion Site Evaluation

By-patient listing of infusion site evaluation and pain at site of infusion as assessed by a visual assessment scale (VAS) will be produced.

9. APPENDICES

9.1. Protocol Schedule of events

Refer to the protocol for a schedule of events.

9.2. Changes from Analyses Specified in the Previous Version of the SAP

Not applicable.

9.3. Sample Size, Power, and Randomization

A sample size of 20 patients from the combined cohorts provides approximately 95% power to detect a mean paired difference in LDH from baseline of -40% at Day 253, with an estimated SD of 45%. This was based on a 2-sided, paired t-test, with a 5% type 1 error rate. To account for a possible 15% dropout rate and additional patients in screening, up to 26 patients will be enrolled.

9.4. Technical Specifications for Derived Variables

The following derived data will be calculated prior to analysis.

Age

Age will be presented as the number of years between date of birth and the reference date. The following ages (in years) may be computed using the formula (reference date – date of birth)+1/365.25, with reference dates indicated as follows:

Table 3: Age and reference date

AGE	REFERENCE DATE
• Age at Enrollment	• Date of Signing ICF
• Age at PNH Diagnosis	• Date of PNH diagnosis
• Age at First Infusion	• Date of First Infusion

For all dates in Table 3, in cases where only the month and year are provided for a date, the day for the date will be imputed as 15. Missing month will be imputed as June. In cases where the day is observed but the month is missing, the date will be imputed as June 15.

Disease Duration

PNH disease duration will be presented as the number of years between the date of first infusion and the date of PNH diagnosis (i.e. $\text{INT}[(\text{Date of first infusion} - \text{Date of PNH diagnosis} + 1)/365.25]$ or a similar formula using months and years or years only in the event of partial dates for PNH diagnosis).

Definition of Baseline Values

Baseline is defined as the last non-missing assessment value prior to the first ALXN1210 dose unless otherwise specified.

Baseline for LDH

Baseline for LDH is defined as the average of all available assessments prior to first ALXN1210 infusion.

Baseline for Electrocardiograms (ECGs)

The mean of the three pre-dose readings on Day 1 for heart rate and RR, PR, QT, and QTcF will be considered the baseline values for each patient. If values are not available for all three readings, an average will be calculated based on the available non-missing values.

Change from Baseline

Change in values from baseline will be calculated as follows.

Change in Value = (subsequent value – baseline value), given that both the baseline value and subsequent value are non-missing.

Percent Change in Assessments from Baseline

Percent change in values from baseline will be calculated as follows.

$$\% \text{ Change in Value} = \frac{\text{Change in Value}}{\text{Baseline value}} \times 100$$

where Change in Value = (subsequent value – baseline value), given that the baseline value is non-missing and non-zero and the subsequent value is non-missing.

ECG Respiratory Rate

For records with missing RR, HR (beats/min) will be used to calculate RR (Milliseconds) as follows:

$$RR = 60000 / HR$$

Adverse Events

Treatment-emergent AEs (TEAEs) are events with start dates and start times on or after the date and time of the first ALXN1210 dose. If the start date of an AE is partially or completely missing and the end (stop) date and time of the AE does not indicate that it occurred prior to first dose, then the determination of treatment-emergent status will be based on the following:

- If the start year is after the year of the first study drug dose, then the AE is treatment-emergent; else,
- If the start year is the same as the year of the first study drug dose and
 - the start month is missing, then the AE is treatment emergent; else if
 - the start month is present and is the same or after the month of the first study drug dose, then the AE is treatment-emergent; else.
- If the start date is completely missing, then the AE is treatment-emergent.

All other AEs are considered Pre-Treatment Adverse Events (PTAEs).

Patient percentages are based on the total number of treated patients in the particular treatment cohort.

Related AEs are defined as possible, probable or definitely related. Unrelated AEs are defined as unlikely or not related.

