7.3.2. Adverse Events (AEs)

Adverse Events (AEs) will be classified by System Organ Class (SOC) and Preferred Term (PT) using the latest available version of MedDRA and will be reported by cohort and overall. The adverse events will be determined as occurring prior to treatment (pre-treatment) or as on or after first treatment (treatment-emergent) as described in Section 9.4. Analyses of Pre-Treatment Adverse Events (PTAEs) and Treatment-Emergent Adverse Events (TEAEs) will be tabulated and presented separately. Patients having multiple AEs within a category (e.g., overall, SOC, PT) will be counted once in that category. For severity/relationship tables, the patient's highest grade/most related event within a category will be counted. Percentages will be based on the number of treated patients in the Safety Set within a cohort and overall. Tables will be sorted by descending frequency of SOC and by descending frequency of PT within SOC.

Listings will be provided for all TEAEs and PTAEs for the Safety Set.

AEs will include the displays described in the following sub-sections

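### Read literally, SAP 9.4 classes an AE dated on the first-dose day with no start time as pre-treatment, although AEs with less complete dates count as treatment-emergent

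*SAP*

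**What the plan says.** SAP Section 9.4 (Adverse Events) works in three layers.

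- Main definition: "Treatment-emergent AEs (TEAEs) are events with start dates and start times on or after the date and time of the first ALXN1210 dose".
- Missing-data rules. The entry condition is "If the start date of an AE is partially or completely missing", joined to a second condition that "the end (stop) date and time of the AE does not indicate that it occurred prior to first dose". Inside this branch an AE is treatment-emergent if its start year is later than the year of first dose, if the year is the same and the month is missing, if "the start month is present and is the same or after the month of the first study drug dose", or if the start date is wholly missing.
- Default: "All other AEs are considered Pre-Treatment Adverse Events (PTAEs".

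A missing start time is not mentioned in any layer. SAP Section 7.3.2 adds no rule of its own. It describes AEs as occurring before treatment "or as on or after first treatment (treatment-emergent) as described in Section 9.4", and then states: "Analyses of Pre-Treatment Adverse Events (PTAEs) and Treatment-Emergent Adverse Events (TEAEs) will be tabulated and presented separately". The same section promises listings of both classes for the Safety Set.

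Protocol Section 15 has AEs recorded from informed consent onward, so Day 1 can hold both pre-dose and post-dose events and the rule has to separate them.

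**The concern.** An AE known to have started on the day of first dosing, but without a clock time, is the case in which the time comparison matters and cannot be made. The section sends it to the pre-treatment class by default. That is the less cautious choice for a safety table, and it runs against the rest of the section, which resolves less precise dates towards treatment-emergent.

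Safety and tolerability are part of the primary objective (Protocol Section 5.1). Protocol Sections 4.1.3.2 and 9.1 name infusion-related reactions as a risk, and Day 1 is every patient's first exposure. SAP Section 5.4.6 records infusion site reactions as AEs, while SAP Section 7.3.3.5 gives the infusion site evaluation itself only a listing. The treatment-emergent AE tables are therefore where such reactions are counted. An event classed as pre-treatment leaves those tables.

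**Working it through.** The plan states no figure on this point, so the check is to apply the rule of SAP Section 9.4 as written and then size one misclassification.

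**Step 1. Apply the rule to start-date patterns.** Take, for illustration, a first dose at 10:00 on the 15th of a month and no stop date or time that places the AE before it. Date and time are compared as one timestamp, so any later date qualifies whatever the time. The last column shows the alternative reading, in which a missing time counts as a partially missing date.

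| Start information | Literal class | Route | Class if a missing time counts as a partial date |
|---|---|---|---|
| Day 1, time after dose | TEAE | main definition | TEAE |
| Day 1, time before dose | pre-treatment | default | pre-treatment |
| **Day 1, time missing** | **pre-treatment** | **default** | **TEAE** |
| Day 2, time missing | TEAE | main definition | TEAE |
| Month of first dose, day missing | TEAE | missing-date rules | TEAE |
| Year of first dose, month missing | TEAE | missing-date rules | TEAE |
| No start date at all | TEAE | missing-date rules | TEAE |
| Complete date the day before first dose, no time | pre-treatment | default | TEAE |

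Row 3 is the gap. Set against rows 5 to 7, it shows the inversion: erase the day from that same AE and it becomes treatment-emergent. A stop date well after dosing does not help row 3, because the stop date is consulted only inside the missing-date branch, which this AE never enters.

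Row 8 shows why the repair must be confined to the first-dose date. Treating every missing time as a partial date would turn an AE known to have started the day before dosing into a treatment-emergent one.

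**Step 2. Size of one misfiled patient.** Planned cohort sizes are 6, 6, 6 and 6 to 8 (SAP Section 4, dosing schedule). The change in a cohort's incidence is 1/n: 1/6 = 16.7 percentage points, or 1/8 = 12.5 points for Cohort 4 at its upper size. SAP Section 7.3.2 counts a patient once per category (overall, system organ class or preferred term). The change therefore appears only if the patient has no other treatment-emergent AE in that category through Day 253 (Day 281 for Cohort 4).

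**Step 3. Context: Day 1 among the infusions in the reporting window.** SAP Section 7.3.1 counts infusions from Day 1 to Day 253, or Day 281 for Cohort 4. With the dosing days in Protocol Table 3:

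- Cohort 1: 2 induction + 8 maintenance + Day 253 = 11, so Day 1 is 1/11 = 9.1%
- Cohort 2: 2 + 5 + Day 253 = 8, so 1/8 = 12.5%
- Cohort 3: 2 + 4 + Day 253 = 7, so 1/7 = 14.3%
- Cohort 4: 1 + 3 + Day 281 = 5, so 1/5 = 20.0%

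These shares describe the schedule. They are neither shares of AEs nor shares of AEs lacking a time, and they do not estimate bias.

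**Step 4. The unknown.** The share of Day 1 AEs without a start time is not in the documents. At 0% the rule has no effect. Protocol Section 15.6 does not list a start time among the recording steps, and Protocol Section 13.5 asks for dates only when describing MAVEs. The case report form is not available, so neither point shows that times are missing.

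**The case against.** The best counter-argument is that the text is under-specified rather than wrong. A programmer working with a single date-time field could take a missing time as partial missingness, enter the fallback rules, and reach treatment-emergent through the same-month bullet. Every outcome listed there is treatment-emergent, so this fits the section's intent. That reading is possible, but Section 9.4 names start dates and start times separately in its definition and refers only to the date when it opens the fallback rules. Applied without limit, the reading also produces the row 8 error. Two readings that give opposite classes are a reason to write the rule down.

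Several further points stand and limit the concern:

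- Section 9.4 treats AE start and stop times as data available for comparison, so wholesale absence of times is not a natural assumption.
- Infusions are supervised (Protocol Section 9.4), with monitoring through 1 hour after the infusion (Protocol Section 9.1) and a further 2-hour stay in clinic up to Day 253 (Protocol Section 10.5). Reactions in that period are witnessed, which makes a missing time less likely without ruling it out.
- Misfiled events remain in the pre-treatment AE tables and listings. Infusion interruptions are summarised separately (SAP Section 7.3.1).
- No formal testing is planned for safety (SAP Section 7.3), and nothing in the documents ties the DMC's escalation reviews to this derivation.

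A reader might infer that first-infusion reactions will disappear from the safety tables, or that treatment-emergent incidence is biased downward by about Day 1's share of infusions. The documents support neither. They give no rate of missing times, and the infusion shares say nothing about that rate.

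**Conclusion.** The defect holds on the literal text. A Day 1 AE lacking only its start time is classed as pre-treatment, while AEs with less date information are classed as treatment-emergent. Neither the SAP nor the protocol contains another rule that catches it. The error runs in the non-conservative direction, in tables that serve the primary objective.

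The consequence is conditional on at least one post-dose Day 1 AE lacking a time and on the programming following the literal text. Where both hold, the effect on a category is at most 16.7 points per misfiled patient in a cohort of 6, or 12.5 points in a cohort of 8, and it is nil for a patient with another treatment-emergent AE in that category. The primary efficacy analysis is untouched.

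Severity is low to moderate: worth correcting because the rule contradicts its own logic and the repair is cheap. The documents do not show that any reported result would be wrong.

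**What to change.** Make two changes to SAP Section 9.4:

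1. Add that an AE whose start date equals the first-dose date and whose start time is missing is treatment-emergent, unless its stop date and time show that it ended before the first dose.
2. Restrict the pre-treatment catch-all to AEs shown to have started, or to have ended, before the first dose.

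Confine the first change to the first-dose date, so that an AE with a complete earlier date and no time stays pre-treatment.

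Also check how the derivation was programmed and list any Day 1 AEs without a start time. If outputs are already final, record the finding in the clinical study report. The note to file appended to the SAP takes that route for another departure in AE tabulation.

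The cost is about a sentence of text and a line of derivation code. The downside is that a few true pre-dose Day 1 events may be counted as treatment-emergent, a small error in the cautious direction.

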9.5. Additional details on Statistical Methods

9.5.1. FACIT-Fatigue (FACIT-FATIGUE) Calculations

The FACIT-FATIGUE questionnaire consists of 13 items scored on a 5-point Likert scale (0=not at all, 4=very much). The FACIT-FATIGUE subscale scoring guideline (version 4) will be used as follows:

All negatively stated items (i.e. all items except An5 and An7 from the CRF) are to be reversed by subtracting the response from 4. After reversing the proper items, all items are summed to obtain a score. The fatigue subscale score is then calculated by multiplying the sum of the item scores by 13, then dividing by the number of items answered. When there are missing data, prorating by subscale in this way is acceptable as long as more than 50% of the items were answered. The score has a range of 0-52 and the higher the score, the better the QOL.

9.5.2. EORTC QLQ-C30 Scoring Calculations

EORTC QLQ-C30 (version 3.0) consists of a total of 30 questions related to QOL, scored on a 4-point Likert scale (1=not at all, 4=very much). It is composed of both multi-item scales and single-item measures. These include five functional scales (physical, role, cognitive, emotional and social), three symptom scales (fatigue, pain, and nausea and vomiting), a global health status and a number of single items assessing additional symptoms (dyspnea, loss of appetite, insomnia, constipation and diarrhea) and financial difficulties. The following explains the scoring procedure.

Table 4: Scoring the QLQ-C30

	Scale	Item range ^a	Item Numbers	Raw Score ^b
Global health status/QoL	QL2	6	29,30	(Q29+Q30)/2
Functional Scales				
Physical Functioning	PF2	3	1 to 5	(Q1+Q2+Q3+Q4+Q5)/5
Role Functioning	RF2	3	6,7	(Q6+Q7)/2
Emotional Functioning	EF	3	21 to 24	(Q21+Q22+Q23+Q24)/4
Cognitive Functioning	CF	3	20,25	(Q20+Q25)/2

	Scale	Item range ^a	Item Numbers	Raw Score ^b
Social Functioning	SF	3	26,27	(Q26+Q27)/2
Symptom Scales				
Fatigue	FA	3	10,12,18	(Q10+Q12+Q18)/3
Nausea and Vomiting	NV	3	14,15	(Q14+Q15)/2
Pain	PA	3	9,19	(Q9+Q19)/2
Dyspnea	DY	3	8	Q8
Insomnia	SL	3	11	Q11
Appetite Loss	AP	3	13	Q13
Constipation	CO	3	16	Q16
Diarrhea	DI	3	17	Q17
Financial Difficulties	FI	3	28	Q28

^a Item range is the difference between the possible maximum and the minimum response to individual items.

^b Raw score is the mean of the component items

Once the raw scores are calculated, a linear transformation to 0-100 is applied to obtain the particular score as follows:

For functional scales: $Score = \{1 - (Raw\ score - 1) / Range\} * 100$

For all other scales/items: $Score = \{(Raw\ score - 1) / Range\} * 100$

Each scale has a range of 0-100%. A high scale score represents a higher response level. Thus a high score for a functional scale represents a high level of functioning but a high score for a symptom scale represents a high level of symptomatology/problem.

Missing data: In the case of multi-item scales missing one of the items, raw scores can still be calculated using the completed items as long as more than 50% of the items were answered. So, for example, if the fatigue scale is missing Q10, the average of Q12 and Q18 would be used to calculate the raw score. For single-item measures, the score will be set to missing.

NOTE TO FILE

Date :	09-May-2022
To :	Biostatistics Study Files
From :	PPD
Cc :	PPD PPD PPD PPD PPD PPD PPD
Protocol #:	ALXN1210-PNH-201
Subject :	Inconsistencies in AE reporting by relationship/severity

Purpose
To document the inconsistencies in AE reporting by relationship/severity between SAP and TLF outputs in the interim analysis (IA) and End of Study (EOS) analysis.

Description of Issue

1) Per SAP v1.0 dated 29 June 2016 Section 7.3 patients having multiple AEs within a category (e.g., overall, System Organ Class (SOC), Preferred Term(PT)) will be counted once in that category. For severity/relationship tables, the patient's highest grade/most related event within a category will be counted.2) However, at IA patients having the same AEs within a severity/relationship category were counted once in that category, which differs from the description in 1).3) Given the small sample size of the study and conservative reporting the general conclusions remain unchanged.

Resolution
To keep consistency across the study, in EOS analysis AE by relationship/severity will be reported in the same way as that in IA. The change of planned analyses will be also documented in EOS CSR.

Prepared By (print name)	PPD
Title	ASSOCIATE DIRECTOR, BIOSTATISTICS (HEMATOLOGY & NEPHROLOGY)
Signature	PPD
Date (dd-mmm-yyyy)	09-May-2022

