## 16.5. Safety Analysis

Safety analyses will be performed on the Safety Set, which consists of all patients who receive at least 1 dose of ALXN1210, and will be reported by cohort and overall. Safety analyses will include all AEs, ECGs, clinical laboratory data, physical examinations, and vital sign measurements, and will be presented using descriptive statistics. No inferential statistical analyses are planned on safety parameters. The incidence of treatment-emergent adverse events and SAEs will be summarized by System Organ Class and Preferred Term for each cohort and overall, by severity, and by relationship to ALXN1210. Adverse events will be coded using the Medical Dictionary for Regulatory Activities, Version 18.0 or higher. Serious AEs and AEs resulting in withdrawal from the study will be listed. Patients having multiple AEs within a category (eg, overall, System Organ Class, Preferred Term) will be counted once in that category. For severity tables, a patient's most severe event within a category will be counted.

Changes from baseline in vital signs and laboratory assessments (chemistry, complete blood count with differential, and urinalysis) will be summarized by cohort. Shift tables of clinical laboratory tests using criteria from CTCAE v4.03 will be produced by cohort. Graphical displays will be presented, as appropriate.

The ECG parameters will be measured at the specified time points, including heart rate, PR, RR, QRS, QT, and corrected QTcF intervals. The average of the triplicate ECG readings at the time points collected will be calculated, and changes from pretreatment baseline values will be assessed by cohort.

All concomitant medications will be coded using the World Health Organization Drug Dictionary, and the frequency and percentage of concomitant medications will be summarized.

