7.3. Safety Analyses

All safety analysis will be conducted on the Safety Set. All safety data available at the time of database lock up to Day 253 (Day 281 for Cohort 4) will be provided in patient listings. AEs will be encoded in the latest available version of standardized Medical Dictionary for Regulatory Activities (MedDRA) and presented by system organ class (SOC) and preferred term (PT). Patients having multiple AEs within a category (e.g., overall, SOC, PT) will be counted once in that category. For severity/relationship tables, the patient's highest grade/most related event within a category will be counted. No formal hypothesis testing will be performed.

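### The note to file keeps an interim AE count in the end-of-study severity and relationship tables that departs from the planned one-count-per-patient rule and can only raise the lower-grade and less-related rows

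*SAP*

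**What the plan says.** **Planned rule.** SAP 7.3 states: "For severity/relationship tables, the patient's highest grade/most related event within a category will be counted". SAP 7.3.2 repeats it. The table-level sections agree. On relationship, SAP 7.3.2.3 says "If a patient has more than one occurrence of an AE, the strongest relationship to study treatment will be used in the summary table"; on severity, SAP 7.3.2.4 says "If a patient has more than one occurrence of an AE, the highest grade will be used in the summary table". Protocol 16.5 has the same rule for severity tables: "a patient's most severe event within a category will be counted". It also plans a summary by relationship, but gives no rule for choosing among a patient's several relationship ratings.

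**What was done and what is intended.** The note to file of 09 May 2022, which follows SAP 9.5.2, reports that "at IA patients having the same AEs within a severity/relationship category were counted once in that category", "which differs from the description in 1" (item 1 being the SAP 7.3 rule). Its resolution is that "in EOS analysis AE by relationship/severity will be reported in the same way as that in IA". It argues that the small sample and conservative reporting leave the general conclusions unchanged, and it undertakes to document the change in the end-of-study report. It gives no counts under the planned rule and does not mention Protocol 16.5.

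**Scope.** SAP section 4 confines the SAP to the report written after the maintenance period (plus Day 281 for Cohort 4). The note nevertheless uses the SAP as its reference for the end-of-study tables.

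**The concern.** Under the planned rule each severity row is the number of patients whose worst occurrence of the event was at that grade. The rows are exclusive and add up to the patients with the event. The interim method, read from the contrast between items 1 and 2 of the note, removes duplicates within a grade or relationship level but not across levels. One patient can then sit in several rows for the same event, and a row means only that a patient had at least one occurrence at that level.

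This can readily happen here. Protocol 15.6 has an AE that later increases in frequency or severity entered as a new AE on a new eCRF line, so a single worsening event can give records of the same term at two grades. For a given patient and event the number of distinct grades recorded cannot fall as follow-up lengthens, and the extension runs up to about 5 years.

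At stake is the severity and relationship profile in the final report. Safety is part of the primary objective and is reported descriptively, without formal testing, so a reader has only the displays to go on.

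**Working it through.** The plan states no figure on this point to reproduce. The check compares the two counting rules.

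**Inputs.** Planned rule: SAP 7.3, 7.3.2, 7.3.2.3, 7.3.2.4 and, for severity, Protocol 16.5. Interim rule: note to file, item 2. Denominators: treated patients in the Safety Set, by cohort and overall (SAP 7.3.2), with planned cohorts of 6, 6, 6 and 6 to 8 and at most 26 patients (Protocol 6, Table 3, and 6.1).

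**General result.** For one Preferred Term, let G(i) be the set of grades recorded for patient i.

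- Planned row: P(g) = number of patients with max G(i) = g.
- Interim-style row: I(g) = number of patients with g in G(i).
- If max G(i) = g then g is in G(i), so I(g) ≥ P(g) in every row.
- The sum of P(g) is the number of patients with the event. The sum of I(g) exceeds it by the sum over those patients of (number of distinct grades − 1).
- At the highest grade seen in any patient, having that grade is the same as having it as the worst, so the two rows are equal there.

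The same argument holds for relationship. In a related/not-related split, the related row is equal under both rules.

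**Severity example (assumed data).** Three patients have the same Preferred Term, with grades {1, 2, 3}, {1, 1} and {2}.

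| Rule | Grade 1 | Grade 2 | Grade 3 | Sum |
|---|---|---|---|---|
| Planned | 1 | 1 | 1 | 3 |
| Interim-style | 2 | 2 | 1 | 5 |

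The excess is (3 − 1) + (1 − 1) + (1 − 1) = 2, and 3 + 2 = 5. Grade 3 is 1 of 3 entries under the plan and 1 of 5 under the interim method.

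**Relationship example (assumed data).** Three patients are rated {not related, related}, {not related} and {related}. Planned: not related 1, related 2, sum 3. Interim-style: not related 2, related 2, sum 4.

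**Can the planned distribution be recovered from the rows?** Take two data sets of two patients each.

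| Grades recorded | Interim-style rows (1/2/3) | Patients with event | Worst grade (1/2/3) |
|---|---|---|---|
| {1, 3} and {2} | 1/1/1 | 2 | 0/1/1 |
| {2, 3} and {1} | 1/1/1 | 2 | 1/0/1 |

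The displayed rows and the any-event total are identical, but the worst-grade distributions differ. So the planned table cannot be rebuilt from the interim-style one.

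**Size of one extra count.** 100/6 = 16.7 percentage points in a cohort of 6; 100/8 = 12.5 in a cohort of 8; 100/26 = 3.8 in the full 26.

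**The case against.** The strongest reply is that this is a disclosed presentation choice that errs on the safe side. Much of that stands. The note names the departure and promises to document it. No row can fall, the row for the highest observed grade is the same under both rules, and so is the related row in a binary split. The tables by SOC and Preferred Term alone (SAP 7.3.2.2) are outside the note, so the stated safety endpoint, incidence of AEs and SAEs, is not affected. By-patient listings are planned (Protocol 16.1, SAP 7.3.2), and with at most 26 patients a determined reader could work out worst grades from them. The number of patients affected could be small or zero.

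The SAP's limited scope also counts: for the end-of-study tables the rule that applies directly is Protocol 16.5, which covers severity only. A reader might infer that the protocol is contradicted on relationship as well. It is not, because it has no most-related rule; that conflict is with the SAP, which the note itself adopts as the standard.

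Three things remain. Disclosure does not supply the planned distribution. The word conservative is only partly apt: no count is lowered, but every extra entry falls in a lower-grade or less-related row, so the displayed mix moves toward milder and less related events. And the claim that conclusions are unchanged cannot be checked from the note, which shows no counts under the planned rule.

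**Conclusion.** The point holds as a departure in counting. The end-of-study severity tables, as the note intends them, conflict with Protocol 16.5; the severity and relationship tables both conflict with the SAP rule that the note takes as its reference. Lower-grade and less-related rows can only be too high, the rows need not sum to patients with the event, and the worst-grade distribution cannot be read back from them. Each extra count is 16.7 percentage points in a cohort of 6 and 3.8 in 26 patients. The total effect is unknown because no output tables are available.

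This rests on reading item 2 of the note as one count per level rather than one per patient, which is the natural sense of its contrast with item 1 but is an inference. It also assumes that some patients have the same AE recorded at more than one level, which Protocol 15.6 makes plausible.

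A reader might go further and infer that severe or drug-related events are hidden, or that the overall safety conclusions are wrong. The documents support neither: the error runs only upward, the top-grade and binary related rows are intact, and nothing shows that the conclusions change. The gap is that the planned displays are missing from the report, and it is cheap to close.

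**What to change.** In the end-of-study report, produce the AE tables by severity and by relationship under the planned rule ("the patient's highest grade/most related event within a category will be counted") over the whole study, as the main display. These tables include the maintenance-period events, so the interim report need not be reissued. Keep the interim-style tables as a supplement, labelled as counting patients with any occurrence at each level. Footnote both sets with the counting rule, and explain why the main tables differ from those reported at interim. Amend the note to file to match and to cite Protocol 16.5 alongside SAP 7.3.

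The cost is a re-run of existing tables with a worst-grade or strongest-relationship flag, plus the footnotes. No new data are needed. The downside is that counts in the main tables will differ from those in the interim report, which the supplement and footnote explain.
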